4. Patients with strength training will activate type II macrophages which are anti-inflammatory and pro-regenerative, tipping the balance away from inflammation towards regeneration when compared to the other treatment groups. Since strength training is likely to initiate signals of muscle regeneration, and since type II macrophages play a key role in this effect, it is possible that increasing the signaling to the muscle for regeneration may also increase the proportion of active type II macrophages which are anti-inflammatory. To test this hypothesis, we will test the proportion of peripheral blood M1/M2 macrophages at baseline, 6 months and 12 months after the initiation of the intervention. Recognizing that immunosuppression may significantly confound this proportion and overall suppress it, we will also test circulating levels of pro-inflammatory cytokines such as C-reactive protein(CRP), IL-6, IL-1, TNF-alpha, homocysteine, adiponectin, leptin, and resistin as well as pro-regenerative cytokines such as TGF-beta and IL-10.

5. We expect patients with strength training will experience less renal dysfunction, decreased hemoglobin A1C, increased peripheral vascular function, decreased fasting blood sugar when compared to the other treatment groups. The rationale for this hypothesis is the finding that muscle mass provides active regulation of glucose and other metabolites. Therefore increasing this may provide improved metabolic function. These laboratory panels are part of the standard transplant follow-up labs and add no cost to the project.

6. Patients with strength training will have an overall improved sense of well-being and energy level compared to those with physical therapy or no treatment. With twice weekly counseling for activity and nutrition, patients will be asked about their general health, mental health and pain intensity using the PROMIS questionnaires.

METHODS

Setting: The study will include 225 patients, to achieve a goal of 180 patients in the GH study group and 45 patients in the control group. Every patient will be followed for 3 years after the start of the intervention. Patients will start the intervention at least 2 months post-transplant; however they can be enrolled prior to transplant.

Main Study Inclusion criteria:

- Successful kidney transplantation (KTx) with primary graft function
- Age between 18 and 65 years

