At baseline, after the patients have fasted overnight, blood samples will be drawn for analyses of pro-inflammatory cytokines such as C-reactive protein (CRP), IL-6, IL-1, TNF-alpha, homocysteine, adiponectin, leptin, and resistin as well as pro-regenerative cytokines such as TGF-beta and IL-10. Peripheral blood M1/M2 macrophages will also be measured. These tests will be performed at baseline, 6 months and 12 months post-intervention. Blood sampling will require approximately 20ml of blood at each blood draw. The total amount of blood drawn will be about 60 ml.

Metabolism and renal function changes

All patients will be monitored for fasting plasma Glucose, HbA1c, Lipid profile (Serum Cholesterol, Triglycerides, HDL Cholesterol, LDL Cholesterol), and serum creatinine during the study per standard of care for kidney transplant patients.

Vascular Function and Vascular Stiffness

Brachial FMD will be used to assess macrovascular endothelial function. This method involves the measurement of vascular reactivity of the brachial artery using non-invasive ultrasound technique. While the subject rests in the supine position, an 11 MHz probe will be used to determine brachial artery diameter above the antecubital fossa in the non-dominant arm. In addition, continuous wave Doppler will be used to determine brachial artery blood flow velocity. Brachial artery diameter and blood flow velocity will be measured under the following conditions: 1) At rest, 2) During reactive hyperemia produced by a five minute interruption of flow with a blood pressure cuff inflated >50mmHg above systolic pressure, 3) For three minutes after reactive hyperemia (30-second intervals for the first minute and 1-minute intervals thereafter).

Assessment of vascular stiffness using peripheral tonometry and ultrasound imaging
Upon entering the lab, participants will be required to rest quietly in the supine position in a dimly lit room for 10 minutes. Arterial size and stiffness will then be measured via ultrasonography using several different methodologies: 1) Pulse wave velocity: this test

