Week 42	1 Warm Up Set: 8 – 12 reps. 1 Heavy Set: 8 – 12 reps. Slower Speed.	Moderate/Heavy	2 minutes
Week 43	3 Sets on each exercise of 6, 8, 12 repetitions. Lower weights each set. Medium speed.	Moderate	3 minutes
Week 44	1 set 90 seconds focused on resistance. Medium speed.	Lighter	2 minutes
Week 45	1 Warm Up Set: 8 – 12 reps. 1 Heavy Set: 8 – 12 reps. Slower Speed.	Moderate/Heavy	2 minutes
Week 46	3 Sets on each exercise of 6, 8, 12 repetitions. Lower weights each set. Medium speed.	Moderate	3 minutes
Week 47	1 set 90 seconds focused on resistance. Medium speed.	Lighter	2 minutes
Week 48	1 Warm Up Set: 8 – 12 reps. 1 Heavy Set: 8 – 12 reps. Slower Speed.	Moderate/Heavy	2 minutes
Week 49	3 Sets on each exercise of 6, 8, 12 repetitions. Lower weights each set. Medium speed.	Moderate	3 minutes
Week 50	1 set 90 seconds focused on resistance. Medium speed.	Lighter	2 minutes
Week 51	1 Warm Up Set 8 reps 1 Heavy Set 8 reps	Heavy	3 minutes
Week 52	Cardio Exercises. 10 exercises in a set. 2 Sets.	Moderate	3 minutes

GH Method: List of Strength/Resistance Exercises

MEN

WOMEN

Exercise

Exercise

Chest: Smith Bench Press/Incline	Glutes: Abductor
Glutes: Abductor	Biceps: Cable Easy Curl / Free Bar
Biceps: Cable Easy Curl/Free Bar	Quads: Leg Extension
Quads: Leg Extension	Chest: Smith Press
Calves: Calf Machine	Abs: Decline
Biceps: Preacher	Quads: Leg Press
Quads: Leg Press	Back: Pull Down Behind
Quads: Leg Extension	Hamstring: Machine
Abs: Decline	Shoulders: Dumbbell Press / Smith Press
Back: Pull Down Behind	Triceps: Push Down / Kick Back / Rope Pull down
Hamstring: Curl Machine	Back: Low Roll
Shoulders: Dumbbell Press / Smith Press	Abs: Sit-Ups
Back: Low Roll	Shoulders: Side Raise with Dumbbells
Hamstring: Good Morning with Dumbbell/ 1 Leg Hamstring Curl	Triceps: Close Grip
Shoulders: Side Rise with Dumbbells	Hamstring: Good Morning with Dumbbells/1 Leg Hamstring
Triceps: Push Down / Kick Back	Triceps: Push Down / Kick Back
Abs: Sit Ups	Abs: Sit Ups
Triceps: Close Grip	Triceps: Close Grip

5)Statistical analyses:

The efficacy of the methods will be determined by:

1. a significant difference in term of pre and post treatment perception of well being between the groups
- 2.a significant difference in the lean/fat body mass ratio between the groups
3. a significant difference in BMI between the groups
4. a significant difference between the inflammatory parameters between the groups
5. a significant difference between the metabolic parameters between the groups

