
The data will be entered into an Excel spreadsheet and stored on the UIMCC hospital server. The patient data, including age, sex, race, underlying kidney disease, length of hospital stay, rejection episode, comorbidities, and medications will be coded and patient names will not be included in the datasheet.

The de-identified collected data will be entered into a SAS database. Initial descriptive analysis will include calculating means, standard deviations, ranges and frequencies. T-tests for continuous variables and Chi Square or Fischer exact tests of association for

categorical variables will be used to compare results of the study between the two groups for the efficacy parameters listed above. A P value<0.05 will be considered significant.

6) Benefits/risks

The main risk of this research is loss of confidentiality of medical information. Consent will be obtained for all patients. Master patient code list will be kept in a separate file accessible only by the primary investigator. A member of the transplant team will be available to answer any questions or discuss any concerns that patients may have.

The patient may experience mild anxiety or discomfort in providing information about their health and well-being. The patient may also have a potential to feel anxiety when being video recorded (if applicable).

Risks associated with the exercise program

The likely risks and discomforts expected in this study are those that largely involve being engaged in an exercise program after a prolonged period of inactivity. Such risks include: strains, sprains, and muscle soreness. Serious physical injury is considered unlikely given the screening for inclusion and physician approval. We will attempt to reduce risks of injury and harm by promoting gradual increases in exercise across time throughout the 3 month period and having exercise be instructed and supervised by trained professional fitness personnel.

Risks associated with the blood draw:

The risks associated with a blood draw include: mild pain, bleeding or bruising at the site of the draw. In general, any bruising should completely disappear within several days. There are minimal risks of fainting or hypotension (low blood pressure) during or after the blood draw.

Risks associated with the Maximal Aerobic Capacity Test (VO2 Test) and the 6 minute walk test include:

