Risks of a muscle tissue biopsy include bleeding, bruising, and infection at the procedure site. A subfascial hematoma (a pocket of blood that forms beneath the fatty layer of the skin next to the muscle) may occur. Medical conditions or use of medications or supplements that causes excessive bleeding creates a higher risk of bleeding from the procedure site. **Risk associated with any surgical procedure include infection. Due to the immunosuppressant drugs these patients are on as part of standard care, this risk may be increased, however the procedure will be done in a sterile environment with a minimal incision to protect against infection.** Less common risks include muscle contracture (shortening of the muscle) and nerve damage leading to loss of feeling at or around the procedure site. Arm may be tender or sore for 2 to 3 days post biopsy. Common side effects of lidocaine include injection site pain, feeling lightheaded, shaking, low blood pressure, drowsiness, confusion, weakness, blurry or double vision, and dizziness. Serious reactions such as seizures, abnormal heart beats, slow heart beat, heart block, severe allergic reactions, respiratory arrest, and coma have occurred.

Benefits

This study is not being done to improve the subject's health. We anticipate that the results of this study will contribute to our understanding of exercise training effects on persons who have had a kidney transplant. It is hopeful that the knowledge gained from this research will benefit others who undergo kidney transplant in the future.

The patients in the supervised physical therapy and GH arms will have the benefit of increased supervision of their physical activity and nutrition compared to what is normally provided per standard of care. In order to assure safety, a medical doctor within the department of surgery who is not affiliated with this research will be appointed to review patient outcomes and monitor the research.

REFERENCES

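### Medications are coded but not used in the comparisons for criteria 4 and 5, and the added cytokines do not address the immunosuppression problem the plan names; the cost is precision, not bias

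*Combined protocol and SAP*

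**What the plan says.** Under Hypotheses, item 4, the plan expects strength training to shift the M1/M2 balance and adds a caution: "Recognizing that immunosuppression may significantly confound this proportion and overall suppress it, we will also test circulating levels of pro-inflammatory cytokines". No other response to the caution appears in the document.

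The section on status of systemic inflammation puts both sets of markers at the same visits: "Peripheral blood M1/M2 macrophages will also be measured. These tests will be performed at baseline, 6 months and 12 months post-intervention". It also says "Blood sampling will require approximately 20ml of blood at each blood draw", with a total of about 60 ml. That equals three draws of 20 ml, so M1/M2 and the cytokines come from one draw per visit. The biopsy risk section confirms that the whole population is exposed: "Due to the immunosuppressant drugs these patients are on as part of standard care".

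Section 5 (Statistical analyses) records that "rejection episode, comorbidities, and medications will be coded". It gives no drug class, dose, visit or date. The comparisons that follow are t-tests for continuous variables and chi-square or Fisher tests for categorical ones. Criterion 4 is a between-group difference in inflammatory parameters; criterion 5 is "a significant difference between the metabolic parameters between the groups". No covariate, stratified analysis or sensitivity analysis uses medications, and the Randomization paragraph names no stratification factor.

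For criterion 5, the section on metabolism and renal function lists glucose, HbA1c, lipids and "serum creatinine during the study per standard of care for kidney transplant patients".

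**The concern.** The plan identifies a factor that may distort one of its outcomes, and its only response is to measure further outcomes exposed to the same factor. It gives no reason why cytokines would be free of the effect of immunosuppression. The variable that could help, medication use, is collected and then left out of the analysis.

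Two things are at stake. Variation due to the regimen stays in the error term of an unadjusted comparison and widens the interval. And with a control arm of 45, the arms can differ by chance in regimen mix; an unadjusted estimate carries that difference with it. The plan does little to make regimens uniform: the Setting paragraph requires at least 2 months since transplant before the intervention starts and gives no upper limit.

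Criterion 5 has the same gap in the analysis, although the plan itself raises immunosuppression as a confounder only for M1/M2.

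**Working it through.** **Inputs from the documents.** 225 patients, randomized 4:1. 225 × 4/5 = 180 and 225/5 = 45, matching the stated split. P < 0.05; sidedness is not stated, so two-sided is assumed. No effect size, SD, power or dropout is given, so the sample size cannot be re-derived.

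**Assumptions.** One binary drug factor with prevalence p, shifting a marker by d, in units of the SD within regimen. The documents give neither p nor d, so ranges are shown.

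**1. Standard error of the difference between arms.** √(1/45 + 1/180) = 0.167 SD. The effect detectable with 80% power is (1.960 + 0.842) × 0.167 = 0.467 SD.

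**2. Chance imbalance.** SD of imbalance = √[p(1−p)(1/180 + 1/45)].

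| p | SD of imbalance (points) | 95% limit (points) | P(imbalance > 10 points) |
|---|---|---|---|
| 10% | 5.0 | 9.8 | 5% |
| 30% | 7.6 | 15.0 | 19% |
| 50% | 8.3 | 16.3 | 23% |

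**3. Precision lost by not adjusting (p = 0.5).** R² = p(1−p)d² / [1 + p(1−p)d²]; the adjusted SE is √(1−R²) times the unadjusted SE.

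- d = 0.3: R² = 0.0225/1.0225 = 0.022; factor 0.989; SE about 1% smaller.
- d = 0.8: R² = 0.16/1.16 = 0.138; factor 0.928; about 7% smaller.
- d = 1.0: R² = 0.25/1.25 = 0.200; factor 0.894; about 11% smaller.

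These figures assume that raw follow-up values are compared. A stable additive drug shift cancels in a change score and is largely absorbed by the baseline marker value, so the further gain from the regimen is then smaller. Section 5 does not say which value criteria 4 and 5 compare.

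**4. Gain from all baseline covariates together.** If baseline marker and regimen jointly explain 10%, 20%, 30% or 50% of the variance (assumed), the detectable effect falls from 0.467 SD to 0.443, 0.418, 0.391 or 0.330 SD. Power at 0.467 SD rises from 80% to 84%, 88%, 92% or 98%.

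**5. Type I error.** In 10,000 simulated trials per setting with no treatment effect, p = 0.5 and d = 0.5, 1.0 or 2.0, the unadjusted t-test rejected in 4.9% to 5.3% and the adjusted model in 4.7% to 5.1%. Leaving out baseline regimen does not inflate the unconditional error. With a true effect of 0.467 within-regimen SD, power was 77% unadjusted against 79% adjusted at d = 0.5, and 70% against 79% at d = 1.0.

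**The case against.** The strongest reply is that randomization already deals with baseline immunosuppression. That is right, and step 5 supports it. A reader of hypothesis 4 might infer that the comparison between arms is confounded; the documents do not support that, because allocation is randomized and the factor is present before the intervention starts.

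A reader might also take an extreme case as typical. At d = 0.8, an imbalance at the 95% limit moves the estimate by 0.163 × 0.8 = 0.13 SD, and the error given that imbalance is about 9%. But only 1 trial in 20 has an imbalance that large, under assumed inputs. The median absolute imbalance is about 0.6745 × 8.3 = 5.6 points, which moves the estimate by 0.056 × 0.8 = 0.045 SD against an SE of 0.167 SD. Over all randomizations the error returns to about 5%.

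For criterion 5, a tempting reading is that clinicians respond to routine results, escalate drugs more in controls, and so hide a benefit. As an illustration with assumed inputs, a true HbA1c effect of −0.4 point with 10 to 25 points more escalation in controls, at 0.8 point each, would show as −0.4 + 0.08 = −0.32 to −0.4 + 0.20 = −0.20. The documents say only that these values are monitored as standard care, not that drugs are changed in response. Such changes would occur after randomization, so baseline covariates cannot remove them. A difference that includes them is also a legitimate comparison of the two policies.

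Finally, hypothesis 4 never claims that cytokines control the confounding. It can fairly be read as adding readouts in case M1/M2 is suppressed. What remains is that those readouts are exposed to the same drugs and that the coded medications go unused.

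**Conclusion.** The point holds as one of precision and robustness. The plan's response to a problem that it names adds outcomes and no control, and the medications it codes enter no analysis of criteria 4 or 5. The comparison is not biased in expectation and its unconditional type I error is not inflated.

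The size is modest: an imbalance SD of 8.3 points at an assumed 50% prevalence (5.0 at 10%), and a standard error that adjustment would reduce by about 1% to 11% for assumed shifts of 0.3 to 1.0 SD, less once the baseline marker or a change score is used. The textual part is firm. The magnitudes rest on assumed prevalence and drug effect, and applying the point to criterion 5 is this review's inference. The change is worth making because it is cheap and can be specified in advance.

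**What to change.** In section 5:

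- Replace the t-test for continuous outcomes under criteria 4 and 5 with ANCOVA of the 12-month value. Adjust for the baseline value of the marker and the immunosuppressive regimen at the pre-intervention baseline visit. Define that visit explicitly, since patients may enroll before transplant.
- For the corresponding metabolic outcomes, also adjust for baseline glucose-lowering or lipid-lowering therapy. State which standard-of-care results count as the baseline and 12-month values, since the text does not tie them to study visits.
- Define the regimen categories in advance; the documents name no drug classes.
- Tabulate medication changes after randomization and rejection episodes by arm, to help interpret the results. Do not enter them as covariates, because the intervention may affect them, and do not claim that baseline adjustment corrects for differential drug escalation.

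In hypothesis 4, reword the sentence so that the cytokines are described as additional outcomes that may themselves be affected by immunosuppression.

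The cost is more than wording: medications must be recorded at the baseline visit, with dates for later changes. No new patient procedure is needed. With the marker and two yes/no drug terms, residual degrees of freedom fall from 225 − 2 = 223 to 220; a regimen with more categories uses a few more.

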Post-transplant, renal function is restored along with appropriate processing of protein and elimination of the catabolic state. Few studies have determined whether restoration of renal function allows the restoration of muscle mass, whether patients are sufficiently strong to accomplish activities of daily living, whether the use of immunosuppressants impedes the ability to increase muscle mass, and whether increasing muscle mass can lead to reduction of medication side effects as has been shown recently with chemotherapy patients. Further, little has been studied regarding protein content of post-transplant diets and its manipulation to increase muscle mass.

Furthermore, although recommendations to engage in physical exercise are routinely made by the Transplant Team, it has been extremely difficult to enroll post transplant recipients in regular exercise programs. Concern with performances, body images,

objective difficulty in performing physical exercise have all contributed to the low level of physical activity typical of this patient population.

The present study aims to analyze the effectiveness of a specific physical activity/nutrition training program (for a detailed description of the GH method see Appendix 1) in comparison to the standard of care for renal transplantations in kidney transplant recipients.

GH METHOD AND PHILOSOPHY

There are four major components of the GH Method (also known as the [name] Method):

- 1) Become experts in our patients.

The GH Method incorporates multiple disciplines including fitness, psychology and nutrition. The efficacy of the GH Method is built around the application of standard processes and curriculum that are then customized to the particular physiology and psychology of each individual patient. For the GH Method to work effectively, we must develop a comprehensive expertise in our patients that demands constant updating as the physiology, psychology and life circumstances of each patient evolves during the program.

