- Adequate cognitive ability to complete the questionnaires, give consent for the study and follow the physical and diet instructions

Main Study Exclusion criteria:

- transplant of any other organ besides kidney alone or a combination of a kidney/pancreas

- non-ambulatory or significant orthopedic problems
- cardiac/pulmonary disease that contraindicate the physical training
- any contraindication to exercise testing per the American Heart Association
- unable to comply with the training program

Muscle Biopsy Inclusion:

- Age between 18 and 65 years
- Patients who have a brachial–cephalic arteriovenous fistula (AVF) in the elbow or brachial–basilic AVF in the arm
- Exercise Arm- the biopsy will only be performed once, after the 12 month exercise intervention is completed (which will be longer than 1 year post transplant surgery)
- Control Arm- this procedure will be performed once, around one year post transplant surgery (may occur at any time during the study)

Muscle Biopsy Exclusion:

- Patients that do not meet the inclusion criteria

Identifying potential subjects for recruitment:

A waiver for an alteration of consent and waiver of documentation of consent is being requested for review of medical records to identify potential patients for study recruitment and also for a telephone screening process for patients that response to a recruitment flyer. The principal investigator already has access to these records as part of daily care for all patients seen in clinic. This presents no more than minimal risk since this data will be kept confidential.

Moreover, as part of the telephone screening process for patients interested in this study there will be oral consent obtained to start the screening process in order to determine if the patients are eligible to be in the study. If the patients are eligible, they will be schedule for a visit where they will be consented to be in the study.

Randomization: All patients who meet the enrollment criteria will be randomized 4:1 to the GH group or the control group.

- GH group: patients will be treated for 12 months with the GH method (Appendix 1) for one hour twice a week

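### Time since transplant has no upper limit at the start of the intervention and enters neither the randomisation nor the analysis, which costs some precision but causes no bias

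*Combined protocol and SAP*

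**What the plan says.** The Setting paragraph under METHODS fixes the earliest start of the intervention and nothing else about timing: "Patients will start the intervention at least 2 months post-transplant; however they can be enrolled prior to transplant". The only transplant-related inclusion criterion, "Successful kidney transplantation (KTx) with primary graft function", carries no time window. The one-year timing in the optional biopsy sub-study does not cap entry to the main study.

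The planned size is stated as follows: "The study will include 225 patients, to achieve a goal of 180 patients in the GH study group and 45 patients in the control group". On allocation, the Randomization paragraph says "All patients who meet the enrollment criteria will be randomized 4:1 to the GH group or the control group". It names no stratum, block or minimisation factor.

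Section 5) Statistical analyses compares the two groups with "T-tests for continuous variables" and chi-square or Fisher tests for categorical ones, at P<0.05. No covariate or regression model is named. Time since transplant is not among the patient data listed there for coding, but that list is introduced as examples, so its absence does not show that the date goes unrecorded.

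The BACKGROUND states "Post-transplant, renal function is restored along with appropriate processing of protein and elimination of the catabolic state". It also says that muscle mass after transplant is little understood and that few studies have settled whether it is restored. Hypothesis 2 expects the transplant itself to leave activity, strength and muscle mass unchanged.

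**The concern.** A patient two months after transplant and a patient many years after it enter the same allocation and the same unadjusted comparison. If the end of the catabolic state leads to some recovery without the GH programme, early patients will change more over 12 months than late ones, whichever arm they are in. That variation stays in the residual of every t-test. With 45 controls, the arms may also differ by chance in their share of early patients, and part of that difference then appears in the estimated effect.

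The spread may be wider still. Enrolment may precede transplant, while PROMIS (Parameters to analyze in all patients) and BMI (Body composition and strength) are first taken at enrolment. As written, one patient's change in well-being could span the transplant itself while another's begins years afterwards.

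**Working it through.** **Inputs from the documents.** 225 patients, 180 GH and 45 control, allocated 4:1; significance at P<0.05 (sidedness not stated, two-sided assumed).

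**Inputs that are assumptions.** 80% power; the share of early patients; the early–late gap in natural 12-month change; and R², the share of outcome variance explained by time since transplant. The documents give none of these.

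**1. The plan's own figure.** 225 × 4/5 = 180 and 225 × 1/5 = 45, which agrees with 4:1. The total of 225 cannot be re-derived, because no effect size, SD, power or dropout is stated.

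**2. Standard error of a between-arm difference, in SD units.** √(1/180 + 1/45) = 0.1667.

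**3. Detectable difference, unadjusted, 80% power.** With t quantiles on 223 degrees of freedom: (1.971 + 0.843) × 0.1667 = 0.469 SD. The normal approximation gives 0.467.

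**4. Chance imbalance.** If half the patients are early, the 95% range for the between-arm difference in that share is ±1.96 × √(0.25 × (1/180 + 1/45)) = ±0.163, or about 16 percentage points. A gap above 10 points arises in about 23% of randomisations.

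**5. Effect on the estimate.** With an early–late gap of 0.5 SD, the shift is at most 0.163 × 0.5 = 0.08 SD at that 95% limit. Relative to the standard error this is 0.08/0.167, about one half.

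**6. R² implied by the same scenario.** For a 50:50 split, R² = 0.25 × gap² = 0.25 × 0.5² = 0.0625, about 6%.

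**7. Gain from adjustment.** The detectable difference is multiplied by √(1 − R²), and the equivalent sample size by 1/(1 − R²).

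| R² (assumed) | Early–late gap needed, 2√R² | Detectable difference | Equivalent extra patients |
|---|---|---|---|
| 0 | 0 | 0.469 SD | none |
| 0.05 | 0.45 SD | 0.457 SD | 5% |
| 0.06 | 0.49 SD | 0.455 SD | 6% |
| 0.0625 | 0.50 SD | 0.454 SD | 7% |
| 0.20 | 0.89 SD | 0.419 SD | 25% |

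**8. Type I error.** Averaged over randomisations, the unadjusted test keeps its 5%. Conditional on a 0.3 SD imbalance in the covariate, which arises in about 7% of randomisations, its error rate is about 6.3% at R² = 0.05 and 9.9% at R² = 0.20.

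**The case against.** Four points can be made against this.

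- **The prognostic role is not established.** A reader might infer from the sentence on the catabolic state that the protocol itself makes muscle recovery depend on time since transplant. It does not. The background gives no time course and calls recovery unresolved, and Hypothesis 2 points the other way. This stands, so the factor can only be called plausible. Hypothesis 2 does not dispose of it, however. It concerns activity, strength and muscle mass, and is silent on well-being, BMI, inflammatory and metabolic parameters, which are four of the five efficacy criteria.
- **The analysis is valid as it is.** This also stands. Randomisation balances the factor in expectation, and the t-test's standard error already allows for chance imbalance. The added noise and the chance shift are one source of variation seen two ways and should not be counted twice.
- **Other covariates have an equal or better claim.** The baseline value of the outcome is an obvious one. That is a reason to include it too, not to omit a date that the trial needs in order to apply its own two-month rule.
- **Some patients may have no value at allocation.** Patients may be enrolled before transplant, and the documents do not say whether randomisation waits. This stands, and the fix has to provide for it.

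**Conclusion.** The point holds as a worthwhile and inexpensive improvement, not as a flaw that invalidates the comparison. The documents confirm that time since transplant has no upper limit, that no stratum is named and that no covariate is used.

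The size is modest and rests wholly on assumptions. With half the patients early and a 0.5 SD gap, the chance shift is at most 0.08 SD at the 95% limit, and adjustment is worth about 6–7% more patients. The gain reaches 25% only at R² = 20%, which for an even split needs a gap of about 0.9 SD; nothing in the documents supports a gap of that size.

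A reader might also infer that pooling early and late patients biases the GH effect. The documents do not support that either, since both kinds of patient are randomised to both arms.

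**What to change.** - **Analysis.** Replace the unadjusted t-tests for the continuous efficacy parameters with a prespecified linear model (ANCOVA) containing arm, the baseline value of the outcome and time since transplant. Fix the value of time since transplant at randomisation, so that allocation cannot affect it. Choose its form in advance, for example log months or early v late with a stated cut-off; a straight line in months over an open-ended range may fit early recovery poorly. Add a category for patients not yet transplanted if randomisation can precede transplant. This also works for patients already enrolled.
- **Randomisation.** For patients still to be randomised, stratify the 4:1 allocation by the same early v late split, using permuted blocks of varying size in multiples of 5.
- **Reconciliation.** Enrolment before transplant (Setting) must be reconciled with the inclusion criterion of a successful transplant with primary graft function, and with the PROMIS and BMI baselines taken at enrolment. State when randomisation takes place and when the clock starts for control patients.

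The cost is one extra stratum to administer and one extra model term. Sample size, eligibility and treatment need not change for the analysis and randomisation steps, and the transplant date should already be on file.
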